each phase, and the total time spent in that phase are detailed below.

- Proximal Prep Phase (Total Time: 7 minutes) All proximal motors, 5-8, are on for the entire phase.
- Distal Prep Phase (Total Time: 7 minutes) All distal motors, 1-4, are on for the entire phase.
- Decongestion Phase (Total Time: 4 minutes) Moving proximal to distal, motor 8 to 1, the motors are turned on for 30 seconds then turned off before moving to the next motor pair.
- Clearing Phase (Total Time: 4 minutes) Moving distal to proximal, motor 1 to 8, the motors are turned on for 30 seconds then turned off before moving to the next motor pair.
- Reabsorption Phase (Total Time: 14 minutes) Moving distal to proximal, motors are turned on at different intensities mimicking a wave pattern.
- The pattern moves up the arm for 16 cycles. Use of this device will not impact standard of care in any way. The participant may ask to stop the research session at any time
- 5. The participant may ask to stop the research session at any timeThe athletic sleeve will then be removed, and a member of the research team will measure the patient's upper limb circumference and induration and administer a survey using the first section of the Lymphedema Life Impact Scale. These measurements are being taken solely for research purposes and should take approximately 3 minutes. Patients will be asked if they experienced any side effects or adverse effects.
- 6. Standardized decongestive therapy will be performed by qualified personnel. This step takes approximately 1 hour and would happen regardless or whether or not patients are enrolled in this study. The exact sequence and modality of therapy varies significantly from patient to patient, but a "typical" treatment session is as follows.

- Treatment today included:
- Manual Therapy provided for 30 minutes:
 - Large Vibration tool (https://www.rehab-store.com/p-magic-wandmassager.html) was applied at moderate pressure/compression on low setting x 3 minutes on each quadrant of the upper extremity covering anterior and posterior side of proximal arm and forearm to decrease pain, inflammation, and protein rich edema.
 - Large Vibration tool was then used to assist in lymphatic flow by using sweeping motion from distal to proximal on the upper extremity.

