 - Example: This IRB application is being submitted on 12/1/21 and the study is collecting data on a standard of care surgery and looking at patient outcomes. All surgeries for this prospective studies will be completed between 1/1/2022 and 1/1/2025. This study will require informed consent UNLESS a waiver of consent is requested and justified.

Attach a copy of your data collection tool or spreadsheet listing exactly what data is to be gathered during this research study.

This research project will collect prospective data. The research team will collect the following specific measurements:

- Upper extremity circumference (measured in centimeters)
- Upper extremity induration
| • Lymphedema Life Impact Scale (LLIS - first section only) | |
|--|-----------------|
| • Any side effects or adverse effects experienced | |
| All measurements will be taken by designated study team members. | |
| Upper extremity circumference will be measured in centimeters at several points, which are: palmar crease, the wrist below the styloid process, wrist + 10 cm, wrist + 20 cm, wrist + 30 cm, and wrist + 40 cm. Upper extremity induration will be measured at the same points as circumference. | |
| Induration will be measured using a durometer (Rex Gauge Co. Model 1600 Dial Durometer Type OO) placed on the aforementioned points on the ventral surface of the proximal forearm. | |
| Lymphedema-related physical complaints will be measured using the first section of the Lymphedema Life
Impact Scale, a validated survey already widely used in the clinical care of lymphedema. | |
| Side effects and adverse effects are thoroughly detailed in section 23.1. Side effects include, but are not limited to, a skin tingling sensation, pain/soreness/swelling, dizziness, headache, nausea, and shortness of breath. | |
| These side effects will be recorded in the Data Collection Tool template inside the secure Carilion Clinic research environment. | |
| 18.4 Describe how long individual participants will be actively in the study. If there will be a period of time after
component of the study where participants will still be in the study (ex: participants outcomes are being ex
medical record at 1 year, but the last research study visit was at 3 months), state this as well. | |
| Patients will be actively participating in the study once a week, for four weeks. | |
| 18.5 Describe how long the entire study is expected to last, including data analysis. | |

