 - Headache is an uncommon occurrence, but it is mild and will subside after treatment has ended.
- Nausea
 - Nausea is an uncommon occurrence, but it is mild and will subside after treatment has ended.
- Shortness of Breath
 - Shortness of breath is an uncommon occurrence, but it is mild and will subside after treatment has ended.

Confidentiality:

Potential loss of confidentiality and release of medical information

Potential of this risk is low since data is shared only with personnel listed in this IRB application and is stored securely in the Carilion Clinic research environment (REDCap, SPARC, and secure Shared Drive). This risk is of moderate seriousness and the duration of the risk is as long as this study is active plus 6 years, as Carilion Clinic SOP stipulates that study data be maintained for 6 years after the conclusion of research activities.

There may also be risks of stress, emotional distress, embarrassment, or inconvenience.

Citations:

- Lerner, R. "Complete decongestive physiotherapy and the Lerner Lymphedema Services Academy of Lymphatic Studies (the Lerner School)." Cancer vol. 83,12 Suppl American (1998): 2861-3. doi:10.1002/ (sici)1097-0142(19981215)83:12b+<2861::aid-ener39>3.0.co;2-v
- 23.2 Define adverse events (AEs), serious adverse events (SAEs), and unanticipated problems (UAPs) for the study. Describe the protocol-specific reporting procedures, including who will be responsible for each step (e.g., PI), timeframes for reporting, how reports will be distributed, and follow-up that will occur.

Ensure that the reporting procedures meet the reporting requirements of Carilion Clinic IRB, the FDA, NIH, OHRP, sponsor, study leadership and any other regulatory body that applies to the study, as applicable. Please note that all Carilion Privacy breaches must also be reported to the Privacy office by the PI. Noncompliance must be reported to the IRB as well as Office of Integrity and Compliance.

Adverse events (AEs):

- Pain, soreness, or swelling in the area being treated or adjacent areas that is NOT alleviated with removing the device
- Headache
- Dizziness
- Nausea
- Shortness of breath
- Skin irritation or rash

Serious adverse events (SAE):

• Infection at the site of treatment

Unanticipated problem (UAP):

• N/A

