For this study, a Data Safety and Monitoring Committee (DSMC) will be established. The committee consists of a physician, lymphedema therapist, and biomedical engineer. They will be familiar with the project, but will have no direct involvement in it. The DSMC will review any reports of anticipated side effects, unanticipated side effects, serious adverse events and unanticipated problems. The study population consists of 15 subjects. Routinely, after each of the first 2 cohorts of 5 study subjects each, the DSMC will conduct a review. The DSMC will only have access to de-identified data. Until this review is completed, and the DMSC makes a recommendation to continue, no subjects will be enrolled and studied. The DMSC will make its determinations based upon review of data that includes the incidence of side effects (physical risks and harms outlined in section 23.1) and incidence of adverse events and serious adverse events (outlined in section 23.2) For occurrence of any unanticipated side effects or adverse events, the study will be immediately suspended, and these conditions will be reviewed by the DSMC, followed by reporting to the IRB. The study will only continue if recommended by the DMSC and permitted by the IRB. Data that will be provided to the IRB if the Stop/Pause is activated will be submitted in writing, and include full disclosure of all data collected, and any written annotations associated with the study in the patient chart. A recommendation of whether the study should continue without modification, continue with modification, or no longer continue from the DSMC will be provided to the IRB in writing after each meeting is held.

23.7 Describe the plans and rationale for conducting an interim analysis.

🔿 Yes 💿 No

23.8 Have stopping rules been established for the study, including for reasons of futility?			
⊙ Yes ○ No			
Describe the stopping rules:			
If any of the following were to occur during the course of the research study, the study will be discontinued.			
 Bleeding or bruising Interference with electronic devices such as, but not limited to, hearing aids and mobile phones Any evidence of increasing edema with use of the device 			
23.9 Are there defined criteria (ex: rates of adverse events) for when study interventions should be discontinue	d?		
⊙ Yes ○ No			
Describe the criteria:			
If any of the following were to occur during the course of the research study, the study will be discontinued.			

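### Section 18.3 refers only to 23.1 for the effects to be recorded, but 23.1 omits two events that 23.2 defines and the DSMC reviews, and no skin observation is scheduled

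*Combined protocol and SAP*

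**What the plan says.** Four sections of the combined protocol and SAP bear on this.

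- **Section 18.3 (data collection).** The item collected is "Any side effects or adverse effects experienced". The text then says "Side effects and adverse effects are thoroughly detailed in section 23.1" and gives examples: "Side effects include, but are not limited to, a skin tingling sensation, pain/soreness/swelling, dizziness, headache, nausea, and shortness of breath". It closes with "These side effects will be recorded in the Data Collection Tool template inside the secure Carilion Clinic research environment". Section 23.2 is not cited.
- **Section 18.1 (procedures).** Step 3 takes arm circumference, induration and the first section of the LLIS before the sleeve goes on. Step 5 repeats these after the device and adds a question: "Patients will be asked if they experienced any side effects or adverse effects". Step 7 repeats them after decongestive therapy and asks about side effects of that therapy. Step 8 repeats the sequence weekly for four weeks. None of these steps includes an inspection of the skin.
- **Sections 23.1 and 23.2 (risks and event definitions).** Section 23.1 lists six physical effects. Section 23.2 lists six adverse events, among them "Skin irritation or rash", and one serious adverse event, "Infection at the site of treatment".
- **Section 23.6 (monitoring).** The DSMC reviews data after each of the first two cohorts of five. It judges the incidence of the 23.1 side effects and, separately, the "incidence of adverse events and serious adverse events (outlined in section 23.2").

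**The concern.** The section that tells staff what to record cites one list, while the section that tells the DSMC what to judge cites two. Someone building or completing the form from 18.3 and 23.1 would meet neither rash nor treatment-site infection by name. These are local events at the site where a vibrating device is worn for 36 minutes, and one of them is the only event the plan classes as serious.

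There is also a question of status. Section 23.6 suspends the study for unanticipated side effects or adverse events. Rash is foreseen in 23.2 but is not among the risks in 23.1, so the text does not settle whether it counts as anticipated.

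The second issue is how a skin event comes to be noticed. The scheduled route is a question to the patient. Without a note of the skin before the device, a reaction seen afterwards cannot be separated from one already there. Without a note afterwards, a mild reaction that the patient does not mention may leave no record. At stake is how a finding of no skin reactions in 15 patients should be read.

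**Working it through.** The plan states no figure on this point, so there is none to reproduce. The check compares the lists term by term and then reads the collection wording against them.

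**1. The lists side by side**

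| Term | Named in 18.3 | In 23.1 | In 23.2 |
|---|---|---|---|
| Skin tingling | yes | yes | no |
| Pain, soreness or swelling | yes | yes | AE, if not relieved by removing the device |
| Dizziness | yes | yes | AE |
| Headache | yes | yes | AE |
| Nausea | yes | yes | AE |
| Shortness of breath | yes | yes | AE |
| Skin irritation or rash | no | no | AE |
| Treatment-site infection | no | no | SAE |

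The named list in 18.3 equals that in 23.1 (6 of 6). Section 23.2 has 6 + 1 = 7 terms and shares 5 labels with 23.1. So 7 − 5 = 2 terms are in 23.2 only, and 6 − 5 = 1 term (tingling) is in 23.1 only. The shared pain item matches by label, but 23.2 adds the condition about removing the device.

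**2. Does 18.3 restrict what is collected?** No. The item covers any effect, and the examples are expressly not exhaustive. The sentence on recording refers back to those open-ended examples, so it cannot be read as limiting the form to six terms. It does not name the 23.2 events either.

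**3. Does the form settle it?** Section 15.4 says the data collection tool is a supplemental document and the REDCap template. It is not in the supplied text. Whether it lists rash, infection or an other field cannot be checked.

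**4. What do the 18.1 steps observe?** At steps 3, 5 and 7 a team member measures the patient's arm. The outputs are circumference, induration and the survey, with a question on effects at steps 5 and 7 only. No output is a skin finding.

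**5. Scale (illustration only).** The documents give no rash or infection rate. At an assumed per-patient rate p, the chance that at least one of n patients has the event is 1 − (1 − p)^n.

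| Assumed p | n = 5 (one cohort) | n = 15 (all) |
|---|---|---|
| 2% | 1 − 0.98^5 = 10% | 1 − 0.98^15 = 26% |
| 5% | 1 − 0.95^5 = 23% | 1 − 0.95^15 = 54% |
| 10% | 1 − 0.90^5 = 41% | 1 − 0.90^15 = 79% |
| 20% | 1 − 0.80^5 = 67% | 1 − 0.80^15 = 96% |

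These figures show how often there would be an event to record, not how often it would be missed. The second quantity needs the probability that an event is captured, and nothing in the documents bears on that. Supplying a value below 1 would assume the answer.

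**The case against.** A reader might infer that the incidences given to the DSMC are likely to be too low, because the six symptoms are prompted by name and rash and infection are left to be volunteered. The documents do not support that.

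- The visible elicitation is one general question applied to every effect. Nothing in 18.1 prompts for headache but not for rash.
- Section 18.3 is worded to collect anything experienced, and 23.6 cites 23.2 directly. Both events are therefore within what is collected and what is reviewed.
- The tool may already name both events.
- There are other safeguards. Staff training on adverse-event documentation is logged (18.6), and a clinically trained team member oversees the sessions and participants are watched closely (23.3). The arm is handled repeatedly, and skin lesions or weeping skin in the treatment area are an exclusion (11.6).

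All of this stands, and it removes any claim that under-counting is likely or can be sized. It does not repair the cross-reference, which is incomplete as written. Nor does it supply a skin record: close watching and arm handling make a reaction easier to see, but no step says that what is seen is written down before and after the device. The exclusion screens for lesions at entry and does not describe the skin at each of four visits.

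**Conclusion.** The point holds as an inconsistency between sections, together with a small gap in ascertainment. Section 18.3 sends the reader to a list that lacks 2 of the 7 events in 23.2, including the sole SAE. That rests on the text alone. Under-counting of those events is possible. It would become a real risk if the unseen tool offered only the 23.1 terms with no free-text field, which the documents do not say. No size can be derived, and the rates in the illustration are assumptions.

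The absence of a scheduled skin observation also rests on the text alone. Its effect could run either way: a reaction missed, or a pre-existing one counted as new. This is a wording correction plus an inexpensive improvement to data capture, not a flaw that undermines the safety review.

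**What to change.** 1. In 18.3, cite both 23.1 and 23.2.
2. Reconcile 23.1 and 23.2 so that each event appears consistently, including tingling (now in 23.1 only) and the differing pain items. State whether the 23.2 events count as anticipated for the purposes of 23.6. Which way that is settled is for the investigator and the DSMC.
3. Confirm that the data collection tool carries every 23.2 term and an other field. If they are absent, add skin irritation or rash and treatment-area infection as yes/no items.
4. Have the team member already measuring the arm at steps 3, 5 and 7 record visible skin findings, so that each visit has an entry before the device, after it and after standard care.

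**Cost.** Wording changes in 18.3, 23.1 and 23.2; at most two rows plus an other field on the form; and a few seconds per reading. With 3 readings at each of 4 visits this is 12 short entries per participant, or 15 × 12 = 180 if everyone completes. The main downside is that more mild redness will be recorded and must be handled under 23.6, so item 2 should be settled before enrolment starts.

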20.0 Research Review of Data/Records			
20.1 What types of records will be reviewed for this research study?			
 Medical record/medical chart Films/x-rays Data in a database Hospital administrative/billing records Quality improvement records Publically available database Other Provide a detailed description about your selection above, including if the records are already in existence at the time of this submission or if you will be accessing future records, and special permissions that may be needed to access the data/records: 			
Carilion Affiliated or VTCSOM Research Team members who have been approved by the IRB to access identifiable information will be reviewing medical records to confirm patient eligibility for this research study. The records that will be used in this study are already in existence at the time of this submission.			
20.2 What is the original purpose of the data being reviewed?			
 Clinical Care Collected as part of routine business activities Research Study Collected under Repository Protocol Other 			
20.3 If collected as part of a previous research study or repository protocol, enter the IRB number for the study.			
N/A			
20.4 Is the data identifiable private information or Protected Health Information (PHI)?			
⊙ Yes ○ No			
21.0 Incidental Findings			
21.1 Does this study involve any imaging procedures (x-rays, CT, MRI, PET, ultrasound, etc.) specifically for research p	urposes?		
O Yes 💿 No			
21.2 Does the research include any of the following?			
 Exams, blood tests, genetic tests or markers, or other tests or procedures that may generate incidental or secondary findings, including disease or conditions other than the one under study, or familial relationships including paternity and ancestry. Testing for communicable diseases None 			

Identification/Recruitment of Subjects

22.1 How do you plan to identify potential subjects?

To "identify" a potential subject refers to procedures to determine which individuals may qualify to participate in the study in order to decide which individuals to contact about taking part.

Check all that apply:

r		a a a a a a a a a a a a a a a a a a a
	Existing Record Review, including Medical Chart Review, Clinic Schedule Review, or QA-QI Database Review.	 Select all that apply: Patients' records reviewed will be those from research team's own patient population Patients' records will be those from other physicians or medical practices' patient population You must request Waiver of Informed Consent and, if any HIPAA identifiers are collected, a Waiver of HIPAA Authorization for recruitment purposes.
	Researchers who ARE NOT treating clinicians of potential subjects will ask treating clinicians for referrals of eligible patients interested in the study.	 Select all that apply: Treating clinicians will identify potentially eligible patients and obtain patient permission before providing researchers with patient contact information. Treating clinician will provide documentation of patient permission in a email/letter to researcher, and researcher must document permission in research record. *You must request a Waiver of Informed Consent/HIPAA Authorization for recruitment purposes.
	Potential subjects will not be directly identified by the researchers from existing records. The potential subject will obtain IRB-approved information about the study from an advertisement, flyer, brochure, website, grand rounds presentation, department meeting, etc. In most cases, the potential	Comments:

subject will contact the researcher if interested.	
Review of Registry/Database in which individuals have previously signed a consent giving their permission to be contacted for future studies.	Comments:
Student Records	Comments:
Other	Please specify other:

22.2 Please describe the identification process.

List all information you plan to collect and record during the identification process PRIOR to contacting potential subjects. This includes the inclusion/exclusion criteria and demographics to determine if a person qualifies for a study before contacting that person to be a potential subject.

- 1. Prior to starting the day, the occupational therapist listed in this application will scan their clinic schedule and identify patients that meet study inclusion/exclusion criteria. This occupational therapist works at both of the locations listed above.
- 2. They will verbally bring up this research study to eligible patients during their regularly scheduled treatment visit, which is typically about an hour long. Lymphedema is treated with a combination of massage and compression, giving the occupational therapist (OT) leeway to talk to a patient while they deliver hands-on treatment. The OT will give a brief explanation of what will happen to the patient and how it will/will not impact their care.
- 3. If a patient expresses interest in participating in the study, the occupational therapist will give them an unsigned copy of the consent document to take home and read over. The OT will verbally confirm that the patient is interested in participating in this study. Additionally, the OT will confirm the patient's contact information (phone number and email address if applicable) and the best time to reach out to them. Then, the OT will reach out to a member of the research team and relay the patient's contact information.
- 4. After receiving the patient's demographics (name and DOB) from the OT, a designated member of the research team (who is Carilion Affiliated or a VTCSOM student and has been approved by the IRB) will access the patient's chart via Epic and confirm their eligibility according to the inclusion/exclusion criteria.

22.3 Through what methods will potential subjects be contacted or recruited?

Check all that apply. To "recruit" a potential subject refers to the initial contact method you plan to use to convey information to a potential subject to determine if he or she would be interested in taking part in your study.

- Direct in-person contact
- Telephone call
- 🔲 Letter
- 🔲 E-mail
- 🔲 Brochure
- Radio/Television script
- 🔲 Newspaper Ad
- Online advertisement (including Facebook, Twitter, Craigslist, other websites, etc.)

Flyer/Poster

Snowball sampling

Clinical trial website posting

🗖 Other

None (there will be no interaction or intervention with potential participants in this study)

22.4 Please provide any additional details about how potential subjects will initially be contacted, who will contact them, or how they will be introduced to the research.

- If recruitment material is being mailed, emailed, or otherwise distributed, describe where/how the distribution list will be obtained.
- If potential subjects will be recruited by telephone, describe how many times the research team will attempt to call / leave a voice message.
- When subjects respond to recruitment material, describe the information that will be provided to them about the study and the information that will be collected from subjects (e.g. name, telephone number, etc.). Describe also, how many times you will attempt to respond to call the subject back / leave a voice message.
- 1. The occupational therapist (provider) listed at the beginning of this application will identify potential participants (based on established inclusion and exclusion criteria) from their patient pool.
- 2. The provider will verbally bring up this research study during a patient's regularly scheduled treatment visit, which is typically about an hour long. Lymphedema is treated with a combination of massage and compression, giving the provider leeway to talk to a patient while they are delivering hands-on treatment. They will give a brief explanation of what will happen to the patient and how it will/will not impact their care.
- 3. If a patient expresses interest in participating in the study, their provider will give them an unsigned copy of the consent document to take home and read over. The provider will confirm that the patient is agreeable to being contacted by the research team and confirm their contact information and the best time to reach out to them. Then, the provider will reach out to a member of the research team and relay the patient's contact information.
- 4. Contact by telephone will only occur once the potential participant has been approached in person and verified interest in the study. Initial contact by phone will only occur by Carilion Affiliated or VTCSOM IRB approved team members unless the participant gives verbal permission to be contacted by a VT Team member, which will then be documented in the research record
- 5. This encounter will be documented as a research note in Epic by a member of the research team.
- 6. Two to three days after the initial contact has been made, a designated member of the research team will attempt to contact the patient via phone call, limiting the number of attempts to three. If the research team member cannot reach the patient during this time, they will not be included in the research study.
- 7. If the study team is able to make contact with the patient, they will have the option to either undergo econsent or choose to sign the consent form at their next regularly scheduled office visit. All consenting procedures will be completed by the Carilion Affiliated or VTCSOM IRB approved team members.

22.5 After potential subjects are identified, describe the pre-screening process that will take place prior to obtaining informed consent.

This could include asking questions to a potential subject to determine whether he or she meets eligibility criteria, for example: patients will answer questions about their medical history, be expected to come to the first screening visit after fasting, stop taking medications, change diet, etc. To comply with HIPAA regulations, only the minimum necessary protected health information may be collected at this time. This means only questions relating to the inclusion and exclusion criteria may be asked.

No prescreening will take place

During the pre-screening process, patients will be asked to confirm their legal name and date of birth (to verify identity). They will also be asked to verify their past medical history, as our inclusion criteria stipulates a current diagnosis of lymphedema. Additionally, patients will be asked about their current health, as our exclusion criteria excludes patients with certain chronic conditions from participating in the research study.

22.6 Indicate whether pre-screening information will be retained on persons who do not ultimately participate in the study and what specific information, including identifiers, will be retained.

Identifiers from patients that decide to not participate in the research study will be maintained on file. This is for the sole purpose of creating a running list so that patients who are not interested in participating are not contacted more than once.

Attach all recruitment materials, letters, phone scripts, flyers, etc. in the Supplemental Documents section after you complete the IRB application.

23.0

Risks and Risk Minimization and Benefits

23.1 List the possible risks, discomforts, or harms to subjects associated with the research.

If the risks differ based on group assignment, describe for each group. Estimate the (1) probability of occurrence, (2) the seriousness, and (3) the duration of each risk. If this information is captured in the protocol or investigators brochure (IB) or other materials, indicate the document and page numbers where the information can be located.

Possible risks, discomforts, or harms include:

Physical: The pressure of the device is less than that of an inflated blood pressure cuff. It is most comparable to a blood pressure cuff that has been well-fitted, but has not been inflated. The device utilizes a level of vibration that has been demonstrated to be similar to devices currently in use by lymphedema therapists. Please see this **link** for a commercially available vibrator that is similar to what is typically used.

- Skin tingling sensation
 - Skin tingling sensation is a common occurrence, but it is mild and will subside after treatment has ended.
- Pain, soreness, or swelling
 - Pain, soreness, or swelling is an uncommon occurrence, but it is mild and will subside after the device is removed and treatment has ended.
- Dizziness
 - Dizziness is an uncommon occurrence, but it is mild and will subside after treatment has ended.
- Headache
 - Headache is an uncommon occurrence, but it is mild and will subside after treatment has ended.
- Nausea
 - Nausea is an uncommon occurrence, but it is mild and will subside after treatment has ended.
- Shortness of Breath
 - Shortness of breath is an uncommon occurrence, but it is mild and will subside after treatment has ended.

Confidentiality:

Potential loss of confidentiality and release of medical information

Potential of this risk is low since data is shared only with personnel listed in this IRB application and is stored securely in the Carilion Clinic research environment (REDCap, SPARC, and secure Shared Drive). This risk is of moderate seriousness and the duration of the risk is as long as this study is active plus 6 years, as Carilion Clinic SOP stipulates that study data be maintained for 6 years after the conclusion of research activities.

There may also be risks of stress, emotional distress, embarrassment, or inconvenience.

Citations:

- Lerner, R. "Complete decongestive physiotherapy and the Lerner Lymphedema Services Academy of Lymphatic Studies (the Lerner School)." Cancer vol. 83,12 Suppl American (1998): 2861-3. doi:10.1002/ (sici)1097-0142(19981215)83:12b+<2861::aid-ener39>3.0.co;2-v
- 23.2 Define adverse events (AEs), serious adverse events (SAEs), and unanticipated problems (UAPs) for the study. Describe the protocol-specific reporting procedures, including who will be responsible for each step (e.g., PI), timeframes for reporting, how reports will be distributed, and follow-up that will occur.

Ensure that the reporting procedures meet the reporting requirements of Carilion Clinic IRB, the FDA, NIH, OHRP, sponsor, study leadership and any other regulatory body that applies to the study, as applicable. Please note that all Carilion Privacy breaches must also be reported to the Privacy office by the PI. Noncompliance must be reported to the IRB as well as Office of Integrity and Compliance.

Adverse events (AEs):

- Pain, soreness, or swelling in the area being treated or adjacent areas that is NOT alleviated with removing the device
- Headache
- Dizziness
- Nausea
- Shortness of breath
- Skin irritation or rash

Serious adverse events (SAE):

• Infection at the site of treatment

Unanticipated problem (UAP):

• N/A

PI will be responsible for reporting any AEs, SAEs, or UAPs.

23.3 Describe the actions that will be taken to minimize the risks associated with participation in this research.

If this research includes risks that might require immediate or prompt medical management, describe access to/availability of emergency medical equipment and trained personnel at each setting where procedures that impart physical/health risks will take place. If this information is available in the study protocol indicate the page numbers where the information can be located.

Participants will be asked verbally whether the external non-clinical team members can be present to perform the research activities. A clinically trained Carilion team member (not an inventor) will be present to perform and oversee all research activities. Clinical research team members may also be present who could provide assistance in a medical emergency. Medical equipment will be present as needed. The participant will be monitored closely during data collection in the clinic. To protect confidentiality research records will be stored on secure and encrypted Carilion Clinic servers.

23.4 For studies involving drugs, devices, biologics, or imaging, describe the type of pregnancy testing that will occur and how frequently it will be conducted on women of reproductive potential.

Include:

- If pregnancy testing will not be conducted, provide the reason.
- State the types of birth control methods women of reproductive potential will be instructed to use.
- If women will not be instructed about acceptable methods of birth control, provide the reasoning.
- Describe the birth control methods men of reproductive potential will be instructed to use. If men will not be instructed about acceptable methods of birth control, provide the reasoning.

While this research study does involve a medical device, there is little evidence to suggest devices and treatment techniques that are similar pose any threat to a woman of reproductive potential. Therefore, this study does not require routine pregnancy testing.

23.5 Does the research include screening tools, questionnaires, or procedures that may indicate the presence of serious depression and/or suicidal ideation?

🔿 Yes 💿 No

23.6 Describe the Data Safety Monitoring Plan or Data Safety Monitoring Board, or indicate the page(s) of the protocol or name of the document where this information can be located. While a robust Data Safety Monitoring Plan is REQUIRED for greater than minimal risk studies, a plan should also be in place for studies that are minimal risk. Please click on the Help circle to the right for information on writing a DSM plan based in risk levels of the research.

Include:

- The data that will be reviewed, including safety data, untoward events, and efficacy data;
- Who is responsible for reviewing the data;
- How the safety information will be obtained and documented (e.g., case report forms, by telephone calls with participants, printouts of laboratory results, etc.);
- The frequency or periodicity of review of cumulative data;
- The statistical tests for analyzing the safety data to determine whether harm is occurring;
- Any conditions that trigger an immediate suspension of the research or other action for the research.

For this study, a Data Safety and Monitoring Committee (DSMC) will be established. The committee consists of a physician, lymphedema therapist, and biomedical engineer. They will be familiar with the project, but will have no direct involvement in it. The DSMC will review any reports of anticipated side effects, unanticipated side effects, serious adverse events and unanticipated problems. The study population consists of 15 subjects. Routinely, after each of the first 2 cohorts of 5 study subjects each, the DSMC will conduct a review. The DSMC will only have access to de-identified data. Until this review is completed, and the DMSC makes a recommendation to continue, no subjects will be enrolled and studied. The DMSC will make its determinations based upon review of data that includes the incidence of side effects (physical risks and harms outlined in section 23.1) and incidence of adverse events and serious adverse events (outlined in section 23.2) For occurrence of any unanticipated side effects or adverse events, the study will be immediately suspended, and these conditions will be reviewed by the DSMC, followed by reporting to the IRB. The study will only continue if recommended by the DMSC and permitted by the IRB. Data that will be provided to the IRB if the Stop/Pause is activated will be submitted in writing, and include full disclosure of all data collected, and any written annotations associated with the study in the patient chart. A recommendation of whether the study should continue without modification, continue with modification, or no longer continue from the DSMC will be provided to the IRB in writing after each meeting is held.

23.7 Describe the plans and rationale for conducting an interim analysis.

🔿 Yes 💿 No

23.8 Have stopping rules been established for the study, including for reasons of futility?			
⊙ Yes ○ No			
Describe the stopping rules:			
If any of the following were to occur during the course of the research study, the study will be discontinued.			
 Bleeding or bruising Interference with electronic devices such as, but not limited to, hearing aids and mobile phones Any evidence of increasing edema with use of the device 			
23.9 Are there defined criteria (ex: rates of adverse events) for when study interventions should be discontinue	d?		
⊙ Yes ○ No			
Describe the criteria:			
If any of the following were to occur during the course of the research study, the study will be discontinued.			
